7. RATIONALE AND BACKGROUND

In the United States (US), renal cell carcinoma (RCC) accounts for nearly 4% of new cancer cases and resulted in an estimated 14,400 deaths in 2017 (National Cancer Institute, 2018).¹¹ Five-year survival for patients with RCC is 74%; however, prognosis varies by disease stage. Among patients initially diagnosed with regional or distant disease, 5-year survival is 67% and 12%, respectively.

Nephrectomy is the recommended treatment for most patients with localized or regional disease, followed by surveillance (Motzer et al., 2017).¹⁰ Although only 16% of patients are initially diagnosed with regional disease, up to 40% will experience relapse with distant metastases following nephrectomy (Janzen et al., 2003; Breda et al., 2007).^{6,2} The high rate of recurrence among these patients highlights a continued unmet need for effective adjuvant treatment that can reduce recurrence risk, prolong the disease-free interval, and/or improve overall survival.

Yet, it is unclear whether postnephrectomy patients in real-world practice settings are typically assessed for recurrence risk postoperatively and whether patients at high risk of recurrence are seen by providers who can evaluate candidacy for adjuvant therapy, clinical trials, or alternative surveillance schedules. Additional evidence is needed to understand postoperative referral patterns and follow-up care for patients at high risk of recurrence.

In this study, researchers at Duke University's School of Medicine and Health System (Duke) and RTI Health Solutions (RTI-HS) will collaborate on a non-interventional, retrospective medical record review study aimed at examining postnephrectomy referral patterns and treatment characteristics in patients diagnosed with RCC. The feasibility of estimating disease recurrence and disease-free interval following nephrectomy in this population will also be explored. Results from this study may provide needed evidence to understand the proportion of postnephrectomy patients who are at the greatest risk of disease recurrence and investigate possible areas of unmet surveillance and treatment needs.

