Exploratory semiparametric Cox proportional hazards models will be used to evaluate factors associated with time to recurrence and overall survival. These outcomes will be defined as described previously. Separate models will be estimated for time to recurrence and overall survival. The models will take the following general form:

$$h(t) = h_0(t) \exp(\beta_1 \text{DEMOGRAPHIC}_i + \beta_2 \text{CLINICAL}_i), \text{ (Equation 2)}$$

Where the following apply:

- $h(t)$ will be the hazard function of recurrence and overall survival as a function of explanatory variables.

- $h_0(t)$ will be the baseline hazard of recurrence and overall survival.
- DEMOGRAPHIC will be a vector of patient demographic characteristics, including but not limited to the following:
 - Age;
 - Sex.
- CLINICAL will be a vector of underlying clinical characteristics, including but not limited to the following:
 - Tumor histology;
 - Type and duration of systemic treatment;
 - Referral status;
 - Subsequent procedures.

The independent variables included in the final Cox proportional hazard models will be selected through an iterative process. First, separate univariate models assessing the relationship between each potential independent variable (eg, tumor histology) and the time-to-event outcome (ie, recurrence and overall survival) will be fit (Klein and Moeschberger, 2005).⁷ The model with the lowest Akaike information criteria (AIC) will be selected for further evaluation. Next, each unselected variable will be added independently to the previously selected model to determine whether the addition of the specific variable results in a lower AIC. The model with the lowest AIC will be selected for further evaluation. This process will be repeated with each of the remaining unselected variables until the addition of unselected variables no longer lowers the AIC. The most parsimonious model will have the lowest AIC. Additionally, variables of clinical significance may be included in the model. The overall goodness-of-fit of the final model will be assessed using Cox-Snell residuals and the proportional hazards assumption for the final set of covariates (Klein and Moeschberger, 2005).⁷

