Cox proportional hazards models will generate a hazard ratio for each of the covariates included in the model, indicating the higher or lower rate of an event (relative to a reference category) at any given point in time following nephrectomy. Like odds ratios from a logistic model, a hazard ratio less than 1 indicates a lower rate of an event, while a ratio greater than 1 indicates a higher rate of an event, relative to a reference category.

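### The exploratory Cox models let referral status and the treatment it can lead to compete in one AIC-selected model, so the final model may give a referral hazard ratio stripped of its treatment-mediated part, or none

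*Combined protocol and SAP*

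**What the plan says.** Section 9.7 (Data Analysis) states the purpose of the models: "Exploratory semiparametric Cox proportional hazards models will be used to evaluate factors associated with time to recurrence and overall survival". Equation 2 has a demographic vector and a clinical one. The clinical vector is introduced as follows: "CLINICAL will be a vector of underlying clinical characteristics, including but not limited to the following". Four items are listed: tumor histology, "Type and duration of systemic treatment", "Referral status" and "Subsequent procedures". Only histology is known at nephrectomy.

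The list is a set of candidates, not a fixed model: "The independent variables included in the final Cox proportional hazard models will be selected through an iterative process". Each candidate is first fitted alone. Variables are then added one at a time for as long as AIC falls, and clinically significant variables may be included as well. On reporting, the section says: "Cox proportional hazards models will generate a hazard ratio for each of the covariates included in the model".

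Section 7 (Rationale and Background), repeated in the abstract, explains why referral matters: it is unclear whether "patients at high risk of recurrence are seen by providers who can evaluate candidacy for adjuvant therapy". The same sentence goes on to name clinical trials and alternative surveillance schedules. Section 9.1 sets the index date at nephrectomy and assesses referral and treatment during follow-up.

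Neither Section 9.7 nor the limitations in Section 9.9 says how a referral hazard ratio should be read when treatment is in the same model.

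**The concern.** On the plan's own reasoning, one thing referral does is bring the patient to someone who can start systemic treatment. A model that holds treatment constant compares referred and non-referred patients with the same treatment, so any association that works through treatment disappears from the referral coefficient. Subsequent procedures could remove a further part in the same way. This would remain even if every exposure were timed correctly and every baseline confounder were adjusted for.

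The selection procedure does not settle the matter. If AIC or the clinical-significance clause keeps both variables, the reported referral hazard ratio is a conditional one, with no label saying so. If treatment enters and referral then fails to lower AIC, the final model says nothing about referral, and a reader may take that as evidence of no association. Referral is in the study's title and is the topic of a primary objective, so a statement that it was not associated with recurrence or survival would attract attention, even from an exploratory model.

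**Working it through.** **The plan's own figure.** Section 9.5 expects 15% to 20% of about 650 patients to be high risk: 650 × 0.15 = 97.5 (98) and 650 × 0.20 = 130. The stated 98 to 130 reproduces. Referral and treatment details are collected only in this subgroup, so it is the set available to these models. The documents give no event count, hazard ratio, referral proportion or treatment proportion; everything below on those rests on assumptions.

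**Mechanism.** Let p1 and p0 be the proportions treated among referred and non-referred patients and θ the treatment hazard ratio. Suppose there is no confounding and referral acts only through treatment. Early in follow-up, the referral hazard ratio without treatment in the model is about

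(1 − p1 + p1·θ) / (1 − p0 + p0·θ).

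Among patients with the same treatment it is 1. Assumed inputs: p0 = 2%, half of patients referred, median time to event 5 years if untreated, censoring uniform from 0.25 to 6 years, treatment coded as a fixed yes/no variable. Cox fits use 300,000 simulated patients per row, except the last.

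| p1 | θ | Formula | Cox, referral alone | Cox, treatment added |
|---|---|---|---|---|
| 20% | 0.76 | 0.952/0.9952 = 0.957 | 0.958 | 1.002 |
| 40% | 0.76 | 0.904/0.9952 = 0.908 | 0.894 | 0.992 |
| 60% | 0.76 | 0.856/0.9952 = 0.860 | 0.850 | 0.993 |
| 20% | 0.60 | 0.920/0.992 = 0.927 | 0.921 | 1.001 |
| 40% | 0.60 | 0.840/0.992 = 0.847 | 0.839 | 1.007 |
| 60% | 0.60 | 0.760/0.992 = 0.766 | 0.754 | 0.993 |
| 60%, p0 = 0 | 0.50 | 0.700/1 = 0.700 | 0.686 | 0.994 |

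The last row comes from a separate simulation of 100,000 patients, with about 45% recurrence at 5 years and 69 months of accrual.

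**Partial mediation.** If referral also has a direct hazard ratio of 0.85 (40,000 patients, same grid of p1 with θ of 0.60 or 0.76), the referral hazard ratio is 0.65 to 0.82 without treatment and 0.85 to 0.87 with it. Only the treatment-mediated part goes.

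**What forward AIC does at the planned size.** Candidates: age, sex, histology, referral, treatment. Inputs: n = 98 or 130, p1 = 40%, θ = 0.60, direct referral hazard ratio 1.0, 0.85 or 0.60, 500 runs per setting, on average about 25 to 41 events.

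- Both kept: about 3% to 9% of runs.
- Referral only: 12% to 43%.
- Treatment only: 28% to 35%.
- Neither: 20% to 53%.

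Next, take the fully mediated case (p1 of 40% or 60%, θ of 0.50 or 0.60, 600 runs per setting) and only those runs in which referral lowers AIC on its own. In 35% to 63% of them, the final model holds treatment and not referral. These last percentages move by several points from one repeat to another.

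**Precision.** At the midpoint of (98 + 130)/2 = 114 patients, in the θ = 0.50 scenario, the standard error of the referral coefficient is about 0.38 alone and 0.46 with treatment added. For a hazard ratio of 0.69: ln 0.69 = −0.371; 1.96 × 0.38 = 0.745; 95% CI exp(−1.116) to exp(0.374), or 0.33 to 1.45. AIC keeps referral in 36% of runs when it stands alone and in 17% once treatment is in.

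**The case against.** The case on the other side is substantial, and most of it stands.

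- A reader might infer that the plan puts both variables into one model. It does not. They are candidates, the clinical-significance clause is optional, and under the assumed inputs AIC kept both in fewer than one run in ten.
- The univariate screening step already fits a referral model without treatment for each outcome. That is so, but the model is unadjusted and the plan does not undertake to report it.
- A reader might infer that the model removes the whole route by which referral acts. Section 7 also names clinical trials and surveillance, and what runs through those stays in the coefficient unless another covariate captures it.
- A reader might infer that a clear referral association would be hidden. An interval of 0.33 to 1.45 in the most favorable scenario shows that it would not be clear in any model of this size. A null finding would mostly reflect imprecision.
- The models are exploratory, concern association, and depend on sufficient sample size (Section 9.1.2). The referral objective in Section 8 is descriptive. A conditional hazard ratio is not an error in itself.
- Referral and treatment both occur after the index date, and Section 9.7 describes no time-dependent or landmark coding. The resulting immortal-time bias is a separate problem and may be larger. A referral model that ignored it would give prominence to a biased estimate.

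What survives is narrower. The two outcomes, a conditional hazard ratio and no hazard ratio, cannot both occur in one model. Either can occur under the plan, however, and neither gives a baseline-adjusted overall referral association. Nothing in the plan warns the reader of this.

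**Conclusion.** The concern holds in limited form. Referral, systemic treatment and subsequent procedures are candidates for the same model, although by the plan's rationale treatment is partly downstream of referral. If treatment is in the final model, the referral hazard ratio is either conditional on treatment or absent. The plan commits to no adjusted, treatment-free alternative.

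The size depends on assumptions that the documents do not supply. With full mediation, no confounding and fixed coding, referral hazard ratios of about 0.69 to 0.96 become about 1.0; with a direct component, the loss is partial. The figures show direction and mechanism, not what this study will find.

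The documents do not support concluding that the study will wrongly report no role for referral, or that a primary objective fails. The consequence is a secondary, exploratory estimate that is open to misreading. The change is still worth making because it is cheap and gives a referral estimate with a defined meaning.

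**What to change.** Add a paragraph to Section 9.7 along these lines:

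*For each outcome, the association with referral status is estimated in a prespecified model containing referral and baseline covariates only. Systemic treatment, its duration and subsequent procedures are left out, and referral is not subject to removal by AIC. Because referral occurs after the index date, it is coded as time-dependent or by landmark. Hazard ratios for treatment come from a separate model, which may include referral. In any model containing treatment, neither the referral hazard ratio nor its absence is interpreted as the overall association of referral with outcome.*

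The baseline covariates should be named in advance from Sections 9.3.1 and 9.3.2 and kept few, given the likely number of events. The cost is this paragraph and one extra model per outcome. No new data are needed: Section 9.3.4 collects referral dates, and Section 10 keeps endpoint timing as days from nephrectomy in the analytic file. It should be confirmed that referral dates are handled in the same way.

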9.1.1. Pilot Phase

To enable assessment of appropriate inclusion criteria and data availability, researchers will conduct an initial pilot study. Duke researchers have compiled a preliminary list of patients diagnosed with RCC who underwent nephrectomy between 01 November 2012, and 31 October 2018, using DEDUCE, Duke's EPIC query tool. A total of 1,069 patients were identified, of which approximately 75% (n = 801) are expected to have been diagnosed with locoregional disease. A total of 883 patients were identified between 01 November 2013, and 31 October 2018 (approximately 662 anticipated to have locoregional disease). At this time, the researchers anticipate that a total sample of approximately 500 patients diagnosed with locoregional RCC who underwent nephrectomy will be required to obtain a sample of 75 to 100 patients considered to have been at high risk for disease recurrence after surgery.

Based on these preliminary counts, it is likely that inclusion of nephrectomies occurring between 01 November 2013, and 31 October 2018, will generate a sufficient sample. Duke researchers will determine preliminary annual aggregated counts, which RTI-HS will use to estimate the anticipated sample size of patients at high risk of recurrence, based on a published algorithm (eg, UCLA Integrated Staging System [UISS] risk status or stage, size,

grade, and necrosis [SSIGN] score) and proportions identified in published literature. Assessing potential sample size during the pilot study will allow researchers to determine whether the proposed sampling strategy (ie, selecting nephrectomy between 01 November 2013, and 31 October 2018) is adequate to obtain the desired sample size. If it is not, nephrectomies occurring from 01 November 2012, may be considered.

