9.5. Study Size

The total sample size will reflect the total number of eligible patients undergoing nephrectomy at Duke University Health System during the study period. At this time, it is estimated that this will be approximately 650 patients. Of this broader sample, it is anticipated that approximately 15%-20%, or 98-130 patients, will be classified as at high risk of recurrence and eligible for additional data collection to document treatment patterns and outcomes. As this study is exploratory in nature, no formal power calculations were conducted to determine the sample size for this study. Furthermore, this study does not

involve formal hypothesis testing and is primarily being conducted to understand clinical characteristics, treatment patterns, and health outcomes. Any significance testing will be exploratory in nature. Thus, the sample size considered for this study should be adequate to address the study objectives.

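### Forward AIC selection from an open-ended list, with hazard ratios reported uncorrected, will often retain noise and will inflate the real effects it keeps

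*Combined protocol and SAP*

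**What the plan says.** Section 9.7 plans separate exploratory Cox models for time to recurrence (recurrence or death) and for overall survival in the high-risk subgroup. Section 9.5 expects that subgroup to be "15%-20%, or 98-130 patients".

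On covariates, Section 9.7 states: "The independent variables included in the final Cox proportional hazard models will be selected through an iterative process". The steps are:

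- Fit every univariate model and carry forward the one with the lowest AIC.
- Add variables one at a time "until the addition of unselected variables no longer lowers the AIC".
- Optionally add clinically important variables, which are not named.

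Six candidate entries are named: age, sex, histology, type and duration of systemic treatment, referral status and subsequent procedures. Both the demographic and the clinical list are expressly left open.

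On output: "Cox proportional hazards models will generate a hazard ratio for each of the covariates included in the model". The only checks on the final model are Cox-Snell residuals and the proportional hazards assumption. The plan gives no expected event count, cap on candidates, shrinkage, resampling or caveat about inference after selection. The limitations in Section 9.9 do not mention it either.

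**The concern.** The same data choose the covariates and then estimate their hazard ratios. A covariate survives because its estimate happened to lie far enough from 1, so surviving estimates are pushed away from 1 on average. Neither planned model check can detect this.

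The AIC rule is also lenient. For a one-parameter term it is equivalent to entry at p < 0.157, so the lowest-AIC model is not especially sparse, although Section 9.7 describes it as the most parsimonious.

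At stake is the list of factors said to be associated with recurrence and survival. Section 9 plans an abstract, a poster and a manuscript from this study. Some listed factors could be noise, and the real ones would look stronger than they are.

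**Working it through.** **The plan's own figure.** Section 9.5 gives about 650 patients, of whom 15% to 20% are high risk: 650 × 0.15 = 97.5 and 650 × 0.20 = 130. This reproduces 98 to 130. The earlier plan on 500 patients gives 75 to 100, as in Section 9.1.1.

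**Events (not stated; assumptions shown).** Section 7 says "up to 40% will experience relapse with distant metastases following nephrectomy". That is a background figure for distant relapse in regional disease, with no time horizon.

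- 40% of 98 to 130: 39 to 52 events.
- 40% read as a 5-year risk, with exponential times, uniform accrual over 5.75 years and a data cut 0.33 to 0.5 year after the last index date: 26.9% to 28.1% have an event, or about 26 to 37.
- 60%, assumed because the endpoint also counts deaths and locoregional recurrences: 59 to 78.
- Deaths for overall survival, from the 67% 5-year survival in Section 7 on the same follow-up assumptions: 22.0% to 23.0%, or about 22 to 30.

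**Noise entry.** A one-parameter term lowers AIC when its likelihood-ratio chi-square exceeds 2, and P(chi-square, 1 df > 2) = 0.1573. This does not depend on the number of events. For k independent null candidates, P(at least one enters) = 1 − (1 − 0.1573)^k:

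- k = 6 (named entries): 64%
- k = 7 (treatment type and duration counted separately): 70%
- k = 8 (assumption): 75%, with 8 × 0.1573 = 1.26 noise terms expected

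These figures include a comparison with an empty model. As written, step 1 keeps the best univariate model regardless, so if every candidate is null the chance of retaining noise is 100%.

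**Coverage for a retained null term.** It is retained when |z| > √2, with probability 0.1573. Its nominal 95% interval excludes 1 when |z| > 1.96, with probability 0.05. Coverage given retention is 1 − 0.05/0.1573 = 68%.

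**Simulation.** Eight independent one-parameter candidates fixed at baseline, 400 runs per row (standard error about 2.5 points on noise retention). The two sizes bracket 75 to 130 patients. The real effects are log hazard ratios of 0.4 per SD (two effects) or 0.3 per SD (four effects).

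| Scenario | n | Mean events | At least one noise term | Coverage, retained null | Coverage, retained real | Mean log HR inflation |
|---|---|---|---|---|---|---|
| All null, empty model allowed | 75 | 30.4 | 75.8% | 65.6% | – | – |
| All null, empty model allowed | 130 | 52.6 | 74.8% | 62.5% | – | – |
| All null, as written | 75 | 30.4 | 100% | 71.1% | – | – |
| All null, as written | 130 | 52.6 | 100% | 68.8% | – | – |
| 2 real, as written | 75 | 31.4 | 65.8% | 62.3% | 93.9% | 1.32 |
| 2 real, as written | 130 | 54.1 | 64.8% | 68.4% | 95.2% | 1.14 |
| 4 real, as written | 75 | 31.4 | 51.2% | 54.8% | 93.0% | 1.57 |
| 4 real, as written | 130 | 54.1 | 56.2% | 62.2% | 95.0% | 1.27 |

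Over all retained terms, coverage was 63% to 71% with all candidates null, 81% to 86% with two real effects and 84% to 89% with four. The same eight covariates fitted with no selection covered 93.5% to 93.9% in every scenario, so selection is the cause.

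**The case against.** The models are labelled exploratory. Section 9.5 disclaims formal hypothesis testing, and none of the five primary objectives in Section 8 depends on a Cox model. Section 9.1.2 makes the exploratory modelling of recurrence conditional on sufficient sample size. Section 9.7 allows clinically important variables to be included. Hazard-ratio intervals are not promised: the 95% intervals in Section 9.7 are for descriptive summaries of continuous variables.

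All of this is correct and lowers the weight of the point. It does not remove it. A label does not correct an estimate, the sample-size condition has no threshold, and hazard ratios printed without intervals carry the same bias.

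Three stronger readings are tempting, and the documents do not support them:

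- A reader might infer that every interval from these models would be too narrow. Retained real effects covered 93% to 95%. The fault lies mainly in estimates displaced from 1, not in their width.
- A reader might infer that noise is retained three times in four. Leaving the step 1 problem aside, that needs eight candidates, all of them null. With four real effects it is just over half.
- A reader might take 39 to 52 as a ceiling on events. The 40% figure is not a planning assumption and covers distant relapse only, while the endpoint is broader.

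**Conclusion.** The point holds as a cheap improvement. Followed as written, the rule always keeps at least one factor. With the six or seven named candidates, noise passes the AIC criterion in 64% to 70% of analyses if all are null; in simulations with eight candidates, at least one noise term was kept in about 51% to 66% of runs when two to four had real effects. A nominal 95% interval for a retained null term covers about 68% in theory (55% to 71% simulated). Retained real effects have log hazard ratios inflated about 1.1 to 1.6 times on average.

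The analytic figures assume independent one-parameter candidates. The simulated figures also assume eight candidates, covariates fixed at baseline and the effect sizes stated. The entry probability does not depend on the event count, so uncertainty about events does not weaken the noise-retention result. Event counts do bear on how many terms each endpoint can support. No primary descriptive estimate is affected.

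**What to change.** For each endpoint, replace selection with one model whose covariates form a closed list, fixed before the updated analysis. Start from age, sex, histology and stage or grade, all of which are already collected. State the expected events for each endpoint and size the list to them, counting parameters rather than variables. Four parameters would have about 10 to 13 events each at 39 to 52 events, but only 5.5 to 7.5 each at 22 to 30 deaths, so overall survival may support fewer. State explicitly whether referral and treatment variables are included, since they are the subject of the study. Report all hazard ratios with 95% confidence intervals.

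If forward AIC is kept as a secondary look:

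- include the empty model at step 1;
- close the candidate list;
- report bootstrap inclusion frequencies only;
- label its hazard ratios as uncorrected for selection.

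Bootstrap percentile intervals should not be used for this. In a one-covariate normal approximation, counting dropped terms as a log hazard ratio of zero means the interval excludes 1 only when |z| > √2 + 1.96 = 3.37. Leaving out the samples where the term was dropped makes the interval of every kept null term exclude 1.

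The cost is protocol wording and a little programming, with no new data. The downside is fewer covariates and possibly less striking associations in an exploratory analysis.

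### The first step of the Cox variable selection omits the no-covariate model, so at least one covariate is always retained for each outcome, even where AIC favours none

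*Combined protocol and SAP*

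**What the plan says.** Section 9.7 (Data Analysis) gives the purpose of the models: "Exploratory semiparametric Cox proportional hazards models will be used to evaluate factors associated with time to recurrence and overall survival". Each outcome has its own selection: "Separate models will be estimated for time to recurrence and overall survival".

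The selection runs in this order:

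- **Start.** "First, separate univariate models assessing the relationship between each potential independent variable (eg, tumor histology) and the time-to-event outcome" are fitted. Then: "The model with the lowest Akaike information criteria (AIC) will be selected for further evaluation".
- **Addition.** After that, "each unselected variable will be added independently to the previously selected model"; the test at this stage is whether AIC falls.
- **Stopping.** "This process will be repeated with each of the remaining unselected variables until the addition of unselected variables no longer lowers the AIC".
- **Stated criterion.** "The most parsimonious model will have the lowest AIC".

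The section then allows clinically important variables to be put into the model as well. It checks the final model with Cox-Snell residuals and an assessment of proportional hazards, and it reports a hazard ratio for every covariate in the model.

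**The concern.** From the second variable onward, a candidate enters only if it lowers AIC against the model already held. The first variable faces no such test. It has to be the best of the univariate models, but it need not improve on a model with no covariates. Nothing later corrects this: the further steps only add variables, the clinical provision only adds variables, and the residual and proportional-hazards checks are not described as removing any.

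Followed literally, the procedure cannot end with an empty model for either outcome. A reader of the report would reasonably assume that a variable described as selected by AIC had passed the AIC test. For the first variable, that test was never made. The candidates include referral status and systemic treatment, which are the study's main subjects, so an unearned place in the model could attract attention.

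**Working it through.** **Inputs from the document**

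- Analysis set: the high-risk subgroup, put at 98-130 patients in section 9.5. This reproduces: 0.15 × 650 = 97.5, rounded to 98, and 0.20 × 650 = 130.
- Named candidates in section 9.7: age, sex, histology, type and duration of systemic treatment, referral status, subsequent procedures. That is k = 6 as listed, or k = 7 if treatment type and duration are separate. The list is expressly open-ended.
- Sections 9.3.1 and 9.3.2 also collect race/ethnicity, TNM stage, grade, tumor size, necrosis, type of nephrectomy and performance status. Adding these seven to the seven above gives k = 14.
- Number of events: not given.

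**Step 1. What the missing test would require.** AIC = −2 log L + 2p, where p is the number of parameters. A one-parameter model has a lower AIC than the no-covariate model only if its likelihood-ratio chi-square exceeds 2. On 1 df, P(χ² < 2) = 0.8427, so the implied entry threshold is p < 1 − 0.8427 = 0.157.

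**Step 2. How often no candidate would pass.** Assume no candidate is associated with the outcome and the candidates are independent with 1 df each. The no-covariate model then has a lower AIC than every univariate model with probability 0.8427^k:

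| k | No-covariate model preferred | Written rule returns no factor |
|---|---|---|
| 5 | 0.425 | 0 |
| 6 | 0.358 | 0 |
| 7 | 0.302 | 0 |
| 10 | 0.181 | 0 |
| 14 | 0.091 | 0 |

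If treatment type has three levels (2 df, penalty 4), P(χ² on 2 df < 4) = 0.8647. With the other six candidates at 1 df, the result is 0.8427^6 × 0.8647 = 0.310.

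**Step 3. Check at the planned size.** Cox data with no true effects were simulated, 600 datasets per setting. The event fractions are assumptions.

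| Patients | Assumed event fraction | k = 6 | k = 7 |
|---|---|---|---|
| 98 | 40% | 0.380 | 0.308 |
| 130 | 40% | 0.355 | 0.277 |
| 98 | 20% | 0.368 | 0.297 |

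The Monte Carlo standard error is about √(0.3 × 0.7 / 600) = 0.019, so these agree with Step 2.

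**Step 4. One real effect.** Suppose one of seven candidates has an expected z of 2 (an illustration, not a figure from the document). It fails the AIC test with probability Φ(1.414 − 2) − Φ(−1.414 − 2) ≈ 0.28. The other six all fail with probability 0.358. Together: 0.28 × 0.358 ≈ 0.10.

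**The case against.** **Staying in the model is not a declared finding.** A reader might infer that the plan is bound to announce a false prognostic factor, or that a retained variable carries no evidence. The document does not support that. Section 9.7 already lets variables enter on clinical grounds without AIC support, and a hazard ratio is reported for each covariate. In the datasets at issue the retained variable has a likelihood-ratio p above 0.157, so its estimate would look weak. This stands, and it narrows the point to what first selection can be taken to mean.

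**The plan may not contradict itself.** The sentence "The most parsimonious model will have the lowest AIC" can be read as ranking only the covariate models defined by Equation 2. That reading is fair, so a flat contradiction should not be claimed. It does not supply the missing comparison: the addition step holds every later variable to a test that the first one escapes. Software that starts forward selection from an empty model would make the comparison, but the plan does not specify this.

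**The 30% figure depends on its assumptions.** It needs all seven candidates to be null at once, and it falls as candidates are added or if any has a real effect. This also stands, which is why a range is given.

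**The gain is limited.** With k = 7 and no true effects, the corrected rule would still select at least one factor in about 1 − 0.302 = 70% of datasets. Those remaining false leads come from AIC selection itself and are not addressed here.

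**Little depends on these models.** They are exploratory. Section 9.1.2 makes exploratory modelling conditional on enough patients, section 9.5 says the study involves no formal tests of hypotheses, and none of the objectives listed in section 8 asks for prognostic factors. This limits the weight of the point, not its correctness.

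**Conclusion.** The point holds in a limited form. As section 9.7 is written, at least one covariate is always retained for time to recurrence and at least one for overall survival, whatever the data show. No other section supplies the missing comparison. First selection therefore does not show that a variable met the AIC criterion.

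If nothing is associated with the outcome and candidates are independent with 1 df each, this matters in about 36% (k = 6), 30% (k = 7), 18% (k = 10) or 9% (k = 14) of datasets per outcome. With one moderate effect among seven it is about 10%. These figures rest on an open-ended candidate list, and nothing in the document makes a complete absence of effects likely. The closed-form figures need no event count. The simulated check assumed 20% or 40% of patients with an event.

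Severity is low: no primary objective, descriptive estimate or Kaplan-Meier result changes.

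**What to change.** In section 9.7, after the univariate fits, add a rule to this effect: *the univariate model with the lowest AIC is taken forward only if its AIC is below that of the model with no covariates, fitted to the same patients; otherwise the report states that AIC selected no factor for that outcome.* Apply it separately to time to recurrence and to overall survival. Clinically important variables may still be added as the plan allows, labelled as not selected by AIC.

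The cost is a sentence or two of text. Standard Cox output already gives the log-likelihood without covariates. If candidates have missing values, the no-covariate model must be refitted to the patients used in the model it is compared with. No new data are needed.
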